## **Participants**

Power analyses showed that 56 people were required for a power of .80 at  $p < .05$ , with a medium effect size (based on previous intervention studies (Robinson et al., 2019) for the analysis of changes in outcome measures from the pretest to the posttest. A total of 80 participants enrolled in the study. Recruitment took place from August 2021 to January 2022, with primary data collection completed in March 2022. Participants were recruited by outreaching to caregiver and older adult organizations, via social media sites, participant recruitment sites (e.g., caregiver forums, registry), and flyers posted in senior centers. Inclusion criteria included family caregivers who are providing care to a loved one (e.g., relative, spouse, friend) who is 65 years or older and is either frail, has a disability, or has confirmed diagnosis of at least one chronic illness (e.g., heart disease, diabetes, arthritis, kidney disease, stroke, ADRD, HIV-AIDS, etc.). Participants also must own an Android smartphone with Google play store/internet access, be familiar with smartphone app usage, able to walk for at least 20 minutes at a time and be comfortable with wearing a Fitbit and using the study-related app. Exclusion criteria included anyone who is currently participating in any other physical activity study/interventions, engages in vigorous exercises for more than 5 hours per week, knows anyone who participated or is currently participating in the study, had a recent cardiovascular event or fall in the past 6 months, or makes more than 2 errors on the Short

Portable Mental Status Questionnaire (Pfeiffer, 1975). Participants kept the Fitbit after completing the study and received \$25 for completing all aspects of the study.

As shown in the consort diagram in Figure 1, a total of 567 potential participants were screened (either by completing an online screening form or by phone call), of which 417 did not meet our eligibility criteria. Of all eligible participants (N=150), 70 did not respond to messages we sent them to schedule a phone call and to receive their oral informed consent. A total of 80 participants gave their oral informed consent and were randomized into either the control condition (n=42) or the treatment condition (n=38). Of the 80 randomized participants, 76 participants completed the pretest and 72 participants started the intervention in one of the three cohorts (cohort 1: n=22, cohort 2: n=22, cohort 3: n=28) to make the social groups manageable, with an equal number of people in each condition for each cohort. Sensitivity analyses were conducted to ensure the baseline characteristics of the three cohorts did not differ from each other. A total of 66 participants (treatment: n=31, control: n=35) completed the posttest.

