## **Data Analyses**

First, we examined all baseline characteristics between both conditions and all three cohorts. To test the research questions, multilevel models (MLM) and the R package lme4 were utilized. Analyses were conducted for the full sample with intent to treat for everyone who completed the pretest (N=76), as missing data in outcome variables could be handled through multilevel analysis. Sensitivity analyses were also conducted for those who had completed both the pretest and posttest, and those results are shown in the tables in the supplementary. Changes in well-being (loneliness, stress, affect, each subscale of caregiver's stress), physical activity (percent change in the number of steps from baseline to the intervention, MCID, minutes active, and each subscale for the self-reported physical activity), and social support (overall social support and each subscale of social connectedness scale), were examined with a 2 (condition) by 2 (time) analysis examining whether the treatment and control conditions differed in the amount and direction of change from the pretest to the posttest controlling for the covariates. We also explored whether there was a condition by time interaction in secondary outcomes for exercise self-efficacy, life satisfaction, and sense of control. In order to conduct more sensitive analyses, we also did planned comparisons because of our *apriori* predictions. Furthermore, multilevel models were tested to examine whether usage of the social features of the app for the treatment group predicted changes in physical activity. Using the PROCESS Macro model in SPSS (Hayes, 2013), mediation models were tested for mechanisms of change for whether increased social support and physical activity in turn led to better well-being. Covariates including app use were included in all mediation models.

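### The 80% power stated for 56 people and a medium effect is not supported for the condition-by-time test, which at that size reaches 80% only for about 0.76 SD of change

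*Combined protocol and SAP*

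**What the plan says.** The Participants section gives the sample size in one sentence: "Power analyses showed that 56 people were required for a power of .80" at the 5% level, "with a medium effect size (based on previous intervention studies", with a citation, "for the analysis of changes in outcome measures from the pretest to the posttest". It gives no numerical effect, effect-size metric, pre-post correlation, sidedness or named test.

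The Data Analyses section sets the main test for well-being, physical activity and social support. Each outcome is "examined with a 2 (condition) by 2 (time) analysis examining whether the treatment and control conditions differed in the amount and direction of change" from pretest to posttest, adjusted for covariates, in multilevel models on the 76 people with a pretest. Those with both pretest and posttest form a sensitivity analysis.

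The flow paragraph under Participants reports 80 randomized (42 control, 38 treatment), and then: "A total of 66 participants (treatment: n=31, control: n=35) completed the posttest".

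**The concern.** The sample-size sentence speaks of change from pretest to posttest. The research question is whether two arms differ in that change. The second is a comparison of two independent groups and usually needs many more people than a test of change within one group. A reader cannot tell which was powered, or what medium means on the scale of the interaction.

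What is at stake is how a null interaction is read. The control arm also gets the Fitbit, the app with its step-linked garden, the workout tutorials and daily reminders (Study Design; Procedure). The contrast is therefore the added effect of the social features. If the 80% figure is taken at face value, a non-significant interaction could be read as fairly strong evidence against a medium benefit of those features.

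**Working it through.** **Inputs.** From the documents: N = 56, power 0.80, alpha 0.05 (Participants); two arms and a difference-in-change test (Data Analyses); 31 v 35 posttest completers (Participants). Assumed because not stated: two-sided test, 1:1 allocation (28 v 28), equal variances, and a pre-post correlation ρ of 0.5 to 0.8.

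**Step 1. Can 56 be reproduced?** The stated inputs do not fix one calculation, so the usual meanings of medium were tried.

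- Within-person change, paired d = 0.5: N = 34, and 56 would give 95.7%. Not 56.
- Two-sample d = 0.5 on change scores: 64 per arm, 128 in total. Not 56.
- One regression coefficient, f² = 0.15: N = 55. At 56 the noncentrality is 0.15 × 56 = 8.4 and power is 81.2%. This fits. Between equal arms it is d = 2√0.15 ≈ 0.77.
- Condition-by-time interaction, f = 0.25, with noncentrality f² × N × 2/(1 − ρ): 34 at ρ = 0.5, 66 at ρ = 0, and 56 at ρ = 0.15 (80.5%). At ρ = 0.15 the effect is 1/√(2 × 0.85) ≈ 0.77 SD of change.
- d = 0.5 in pretest SD: fits if ρ is about 0.785 (Step 3).

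**Step 2. Power of the test of difference in change.** Power is the chance that a noncentral t on n₁ + n₂ − 2 degrees of freedom exceeds the two-sided 5% critical value, with noncentrality d√(n₁n₂/(n₁+n₂)) and d in SDs of the change score.

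- 28 v 28: √14 = 3.742. At d = 0.5 the noncentrality is 1.871 and the critical value 2.005, so power is 45.1%. Power of 80% needs d = 0.762.
- 31 v 35: √(1085/66) = 4.055. At d = 0.5 the noncentrality is 2.027 and the critical value 1.998, so power is 51.5%. Power of 80% needs d = 0.702.

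**Step 3. If medium means 0.5 pretest SD.** With equal variances at the two times, the SD of change is the raw SD × √(2(1 − ρ)), so d = 0.5/√(2(1 − ρ)). If the posttest is instead adjusted for the pretest, d = 0.5/√(1 − ρ²).

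Correlation needed for 80% at 28 v 28:

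- Change score: 1 − ρ = 0.125/0.762² = 0.215, so ρ = 0.785.
- Baseline-adjusted: ρ = √(1 − (0.5/0.762)²) = 0.755.

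| ρ | d, change score | Power 28 v 28, change | Power 28 v 28, adjusted | Power 31 v 35, change | Power 31 v 35, adjusted | Total N for 80%, change |
|---|---|---|---|---|---|---|
| 0.5 | 0.500 | 45% | 56% | 51% | 64% | 128 |
| 0.6 | 0.559 | 54% | 63% | 61% | 70% | 104 |
| 0.7 | 0.645 | 66% | 73% | 73% | 80% | 78 |
| 0.8 | 0.791 | 83% | 86% | 88% | 91% | 54 |

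**Step 4. Common scale.** The three readings in Step 1 that give about 56 correspond to 0.77, 0.77 and 0.76 SD of change between arms. That is no coincidence: with 28 per arm and a two-sided 5% test of change scores, 80% power is reached at about 0.76 SD however the effect is labelled.

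**The case against.** A reader might infer that the 80% figure is simply false, or that the sponsor made an arithmetic error. The documents do not support that. Medium is never defined and is tied to a cited source that is not available here. Three conventional readings do give about 56 for a one-degree-of-freedom interaction, and f² = 0.15 is a natural choice where regression-type models are used. Converting it to 0.77 SD shows that this medium is a large between-arm difference. It does not show that the calculation was wrong. The sentence may also have been meant for within-person change, or for the planned comparisons, whose content is not described. This part of the objection stands, and the point has to be conditional.

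The change-score figures may also be pessimistic. The analysis adjusts for covariates, and if the pretest is among them, power at 31 v 35 for 0.5 pretest SD is 64% to 91% rather than 51% to 88%. That stands too, so both ranges are given.

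The trial also passed its target of 56, and the main analysis uses 76 people. This helps less than it seems. Even if all 76 had complete data and were split 38 v 38 (an assumption), power for 0.5 SD of change would be about 58%. A one-sided test would not rescue that effect either: 58% at 28 v 28.

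Finally, no section interprets a null result. The over-reading is a risk, not something the documents have done.

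**Conclusion.** The power statement is not supported, as written, for the test that answers the research questions. At 56 people that test has 80% power only for about 0.76 SD of the change score, and with 31 v 35 for about 0.70 SD. The 45% and 51% figures apply only if medium means 0.5 SD of change. If it means 0.5 pretest SD, the claim needs a correlation of at least about 0.785 (about 0.755 with baseline adjustment) that the plan does not state and that would have to hold across many outcomes.

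These figures assume a two-sided 5% test, 1:1 allocation at N = 56, equal variances and no gain from covariates other than the pretest. The detectable differences do not depend on what medium was meant to be. This is a correction to reporting and interpretation. It does not call for a change in conduct or in the analysis model.

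**What to change.** 1. Keep the planned calculation on record and complete it: numerical effect, scale (SD of change, pretest SD, f or f²), assumed pre-post correlation, sidedness, and whether it was for within-person change or the condition-by-time interaction.
2. Add, for the condition-by-time test at two-sided 5%: the difference detectable with 80% power is about 0.76 SD of the change score at N = 56 and about 0.70 SD at 31 v 35. Power for 0.5 pretest SD at 31 v 35 is 51% to 88% for correlations of 0.5 to 0.8, or about 64% to 91% if the posttest is adjusted for the pretest.
3. Report each condition-by-time interaction as an estimate with its 95% confidence interval, and do not present a non-significant one as 80%-powered evidence against a medium effect.

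No further enrolment is proposed. The cost is wording only, with a less favourable stated power.

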## **Study Design**

The social exergame app, Go&Grow, could provide physical, social, and health benefits for family caregivers because of its simple interface for physical activity-related gamification (flowers can be selected and will grow based on the user's completion of daily step goals) and social contact features (users can post stories, share virtual gardens, and react to other users' stories). Participants could also follow workout tutorials implemented to Go&Grow from the National Institute of Health (NIH) Go4life (National Institute on Aging at NIH, 2020), and log and track their workouts on a daily and weekly basis (Figure 2). More details on the description of the full Go&Grow app can be found in the Lin et al., 2020 paper. Each day, the app sent notifications

to remind participants to use the app and asked participants to rate their daily mood using a mood slider.

The treatment group (social exergame condition) used the full version of Go&Grow with the social contact features, which allowed users to view, like, reply to, post a story, and view other users' gardens. They also received in-game rewards (unlock new flowers to grow each week) if they posted stories. The control group (exergame non-social condition) used Go&Grow without the social contact features; therefore, they were not able to unlock new flowers (Figure 2).

### **Procedure**

The current study was a two-armed randomized control trial with a pretest (baseline week 1 and 2), weekly assessments at the end of each week (week 1 to 8), and a posttest (after week 8). All participants were blinded to their conditions. Both groups received the same frequency of contact from researchers and followed the same procedures throughout the study period.

All contact and data collection were done remotely. Participants who were interested in joining the study were instructed to fill out an online screening form which included the screening items for inclusion and exclusion criteria. If participants were eligible based on the screening, a research assistant reached out to the participant within three days to obtain informed consent. Participants received a copy of the informed consent through email during the informed consent process. Research assistants went over the informed consent with participants over the phone and participants provided consent orally. Once participants agreed to take part in the study, research assistants sent participants a link to complete the demographic survey (including covariates) and the pretest. Upon completion of the demographic survey and the pretest, participants were shipped a Fitbit Inspire 2 tracker, instruction materials, a face mask, and a stylus pen to their home postal address.

**Session 1 (Pretest).** A research assistant trained the participants in both conditions to use the Fitbit by phone and with an instructional manual, an approach that has been effective in previous studies (Bisson et al., 2021; Robinson et al., 2019).

**Week 1-2 (2-Week Baseline).** Participants in both conditions would wear the Fitbit for two weeks to obtain baseline steps. Both conditions also completed a weekly survey for weeks 1 and 2. Each measure collected during this period was averaged to create a baseline score.

**Week 3 – 8 (6-Week Intervention Period).** On the first day of week 3, research assistants trained participants on how to use Go&Grow with the instructional guide and phone consultation for both conditions. After the training, participants in both conditions started using the app while continuing to wear the Fitbit for 6 weeks. They were reminded daily with app-based notifications to wear their Fitbit and use the Go&Grow app. The reminder for the treatment condition also included the message: “Don’t forget to share your stories to unlock new flowers”. Participants continued completing weekly surveys for 6 weeks.

**After week 8 (Posttest).** All participants completed a posttest, which was the same as the pretest.

## **Measures**

The current study consisted of measures from the pretest, weekly assessments at the end of each week (week 1 to 8), and a posttest (after week 8). The same measures were used for both conditions. All questionnaires were administered through Qualtrics links sent to each participant via the Eztexting platform or through email. Participants' electronic data (steps and app usage data) were collected using a secure server from Brandeis University, and the data were kept confidential.

## **Data Analyses**

First, we examined all baseline characteristics between both conditions and all three cohorts. To test the research questions, multilevel models (MLM) and the R package lme4 were utilized. Analyses were conducted for the full sample with intent to treat for everyone who completed the pretest (N=76), as missing data in outcome variables could be handled through multilevel analysis. Sensitivity analyses were also conducted for those who had completed both the pretest and posttest, and those results are shown in the tables in the supplementary. Changes in well-being (loneliness, stress, affect, each subscale of caregiver's stress), physical activity (percent change in the number of steps from baseline to the intervention, MCID, minutes active, and each subscale for the self-reported physical activity), and social support (overall social support and each subscale of social connectedness scale), were examined with a 2 (condition) by 2 (time) analysis examining whether the treatment and control conditions differed in the amount and direction of change from the pretest to the posttest controlling for the covariates. We also explored whether there was a condition by time interaction in secondary outcomes for exercise self-efficacy, life satisfaction, and sense of control. In order to conduct more sensitive analyses, we also did planned comparisons because of our *apriori* predictions. Furthermore, multilevel models were tested to examine whether usage of the social features of the app for the treatment group predicted changes in physical activity. Using the PROCESS Macro model in SPSS (Hayes, 2013), mediation models were tested for mechanisms of change for whether increased social support and physical activity in turn led to better well-being. Covariates including app use were included in all mediation models.

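### At least 10 main outcomes get the same condition-by-time test, with no primary named among them and no multiplicity rule in the available text, so the chance of a false-positive claim exceeds 5%

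*Combined protocol and SAP*

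**What the plan says.** The Data Analyses section lists outcomes in three domains:

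- Well-being: the list opens "Changes in well-being (loneliness, stress, affect, each subscale of" and ends with caregiver stress. Four entries, one of them a set of subscales.
- Physical activity: percent change in steps, then "MCID, minutes active, and each subscale for the self-reported physical activity". Four entries, one a set of subscales.
- Social support: "overall social support and each subscale of social connectedness scale". Two entries, one a set of subscales.

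All of these "were examined with a 2 (condition) by 2 (time) analysis examining whether the treatment and control conditions differed" in the amount and direction of change. The section then explores a "condition by time interaction in secondary outcomes for exercise self-efficacy, life satisfaction, and sense of control". It goes on: "In order to conduct more sensitive analyses, we also did planned comparisons because of our" a priori predictions, without giving the contrasts or the outcomes. Two further sets of analyses follow. In one, "multilevel models were tested to examine whether usage of the social features of the app for the treatment group predicted changes" in physical activity; the other consists of mediation models.

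The only significance level in the documents is p < .05, in the power statement under Participants. That statement is "for the analysis of changes in outcome measures from the pretest to the posttest", in the plural, and names no single outcome. The word primary occurs only in relation to data collection.

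**The concern.** Labelling three outcomes secondary implies that the three listed domains are the main ones. Within those domains nothing says which outcome carries the trial's conclusion, and no correction, hierarchy or gatekeeping rule appears. On the text as it stands, one significant subscale out of ten or more could be presented as the effect of the social features.

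From the available text a reader could not count the tests from which that result was drawn, because neither the subscales nor the planned comparisons are enumerated. The planned comparisons are offered as a more sensitive analysis, so they add further chances of a positive finding.

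**Working it through.** **The plan's own figure.** The required sample of 56 can be neither confirmed nor refuted, because a medium effect is given no metric and no pretest-posttest correlation is stated. A single regression coefficient with f² = 0.15 needs 55. The 2 by 2 interaction with f = 0.25 needs 56 at a correlation of 0.15 and 34 at 0.5. A plain two-arm comparison with d = 0.5 needs 126. The point does not depend on this figure.

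**Count.** There are seven single entries: loneliness, stress, affect, percent change in steps, MCID, minutes active and overall social support. There are three subscale sets: caregiver stress, self-reported physical activity and social connectedness.

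- Each set counted once: 7 + 3 × 1 = 10.
- Two subscales per set: 7 + 3 × 2 = 13.
- If MCID is derived from steps, which is not stated: 9 or 12 distinct outcomes.

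The secondary outcomes, planned comparisons, app-usage models and mediation models are left out.

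**Formula.** Assume two-sided .05 per test and no true effects. For k independent tests, the chance of at least one p < .05 is 1 − 0.95^k:

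- k = 10: 1 − 0.95^10 = 0.401
- k = 13: 1 − 0.95^13 = 0.487

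For normal test statistics with common correlation ρ, it is 1 − ∫ [Φ((c − √ρ·g)/√(1−ρ)) − Φ((−c − √ρ·g)/√(1−ρ))]^k φ(g) dg, with c = 1.96. For benefit only, the lower term is dropped, so a single test has a rate of 2.5%. The documents give no correlations, so a range is shown.

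| Assumed correlation | k = 10, two-sided | k = 13, two-sided | k = 10, benefit only | k = 13, benefit only |
|---|---|---|---|---|
| 0 | 0.401 | 0.487 | 0.224 | 0.280 |
| 0.3 | 0.351 | 0.418 | 0.178 | 0.214 |
| 0.5 | 0.287 | 0.334 | 0.144 | 0.167 |
| 0.7 | 0.213 | 0.241 | 0.107 | 0.120 |
| 0.9 | 0.128 | 0.138 | 0.064 | 0.069 |
| 0.7 within, 0.3 between domains (simulated) | 0.289 | 0.332 | 0.145 | 0.169 |

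The last row uses domain blocks of 4, 4 and 2 entries for k = 10, and 5, 5 and 3 for k = 13. With 9 or 12 outcomes the two-sided figures are 0.370 and 0.460 if independent, and 0.124 and 0.135 at correlation 0.9.

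**Effect of adjustment.** This was simulated with t-tests on 31 v 35 completers (the posttest numbers under Participants), correlation 0.3 and three truly different outcomes. For 10 and 13 outcomes, with true effects of 0.5 to 0.7 SD, the chance of any false positive is:

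- unadjusted: 27% to 35%
- Benjamini-Hochberg at .05: about 6% to 9%
- Holm: about 4%

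With no true effects, Benjamini-Hochberg gives about 3% to 5%.

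**The case against.** Five points deserve weight.

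- **Correlation.** Subscales of one instrument are correlated, so the independence figures of 40% to 49% are an upper end. A reader might take them as the trial's error rate, or say that the rate is well above 5% whatever is assumed. The documents do not support either reading: they give no correlations, and the benefit-only figure falls to about 6% at correlation 0.9. What stands is that every case exceeds 5%, and that the benefit-only figures compare with 2.5% for one test.
- **Decision rule.** The figures assume that any single p < .05 becomes a claim. The documents do not say this, but they state no other rule.
- **Missing text.** A reader might infer that the trial never had a primary outcome or a hierarchy. That does not follow. Some text was removed before review, the Measures section as available lists no instruments, and the analysis section refers to research questions, a priori predictions and supplementary tables that are not shown. The point holds for the available text only.
- **Partial ranking.** Three outcomes are called secondary, so the list is not wholly unranked. The main outcomes are still unranked among themselves. The plan tests individual outcomes and subscales rather than three domain scores; even three independent tests would give 1 − 0.95³ = 14.3%.
- **Choice of remedy.** Benjamini-Hochberg controls the false-discovery rate, which is not the chance of any false positive. Separate families by domain could also be defended. The choice must follow from the claim to be made.

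**Conclusion.** The concern holds in limited form. The available text puts at least 10 main outcomes through one test without ranking them, naming a primary or stating a multiplicity rule. For 10 to 13 outcomes, the chance of at least one false positive is about 13% to 49% two-sided, and 29% to 33% if correlations are 0.7 within and 0.3 between domains. For benefit only it is about 6% to 28%.

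These figures rest on four assumptions: .05 applied to each test (inferred from the power statement), no true effects, any p < .05 being claimed, and the assumed correlations. They do not show that any particular result is false, and they do not invalidate the trial. They show that an unadjusted claim drawn from this list would carry more than the nominal error.

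**What to change.** 1. Treat all well-being, physical activity and social support outcomes in the Data Analyses section as one family, with every subscale counted and named. Report multiplicity-adjusted beside unadjusted p-values for their condition-by-time tests.
2. Use Holm if the claim is that any single outcome changed. Use Benjamini-Hochberg at .05 if false-discovery control is accepted, and state that it does not hold the chance of any false positive to 5% when some effects are real.
3. Label the three secondary outcomes, the app-usage models and the mediation models exploratory.
4. List each planned comparison with its outcome and contrast. One that is the between-arm contrast in change for a family outcome is the same test and belongs in the family. All others are exploratory, and no within-arm change is evidence of a social-feature effect.
5. Data collection ended in March 2022, so disclose any primary outcome named now as post hoc unless an earlier dated record shows that it was prespecified.

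**Cost.** No new data and no refitting of the main models: adjusted p-values come from the models already fitted. Prespecification cannot be restored.

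The downside is lower power for adjusted claims. As an illustration from completer t-tests without covariate adjustment (31 v 35, correlation 0.3, 3 of 10 outcomes truly different), power per outcome is:

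| True difference | Unadjusted for multiplicity | Benjamini-Hochberg | Holm |
|---|---|---|---|
| 0.5 SD | 0.51 | 0.25 | 0.21 |
| 0.7 SD | 0.80 | 0.58 | 0.49 |

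The loss under the covariate-adjusted multilevel model with N = 76 may be smaller. Suppose instead that the plan's 0.80 power at 56 people is taken as given. Power at .05/10 = .005 (Bonferroni, the level of Holm's first step) is then Φ((1.960 + 0.842)·√(N/56) − 2.807). That is about 59% at N = 66 and 68% at N = 76, against 86% and 90% at .05. Unadjusted results stay visible throughout.

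### The condition-by-time interaction is valid but gives each arm its own pretest mean; a common pretest mean with an unstructured covariance would usually be more precise

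*Combined protocol and SAP*

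**What the plan says.** Data Analyses states that changes in well-being, physical activity and social support "were examined with a 2 (condition) by 2 (time) analysis examining whether the treatment and control conditions differed in the amount" and direction of change between the two tests, adjusted for covariates. The models are multilevel models in lme4, fitted "with intent to treat for everyone who completed the pretest (N=76"). The section does not name the covariates or say how they enter. It adds: "In order to conduct more sensitive analyses, we also did planned comparisons". Those comparisons are not defined.

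On numbers, Participants reports that 80 people "were randomized into either the control condition (n=42) or the treatment condition (n=38"). It continues: "Of the 80 randomized participants, 76 participants completed the pretest and 72 participants started the intervention" in three cohorts (22, 22 and 28), "with an equal number of people in each condition for each cohort". Finally, "A total of 66 participants (treatment: n=31, control: n=35) completed the posttest". Procedure says that participants were blinded, that the Fitbit was shipped only after the pretest, and that app training came on the first day of week 3.

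**The concern.** In the 2 by 2 model the pretest is one of two responses, and each arm has a free mean at each time. The interaction is then the difference between arms in mean change. Under randomisation, with blinded participants who had not yet used the app, the expected pretest means are equal. Estimating them separately carries chance pretest imbalance into the treatment estimate at full weight. A model with one common pretest mean weights that imbalance by the regression of posttest on pretest, and so is generally more precise.

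The plan asks for more sensitive analyses, and only 66 people have a posttest. Precision available from data already collected is therefore worth having for the between-arm question. Nothing here suggests that the interaction is biased.

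**Working it through.** **Inputs.** Randomised 38 treatment and 42 control; 76 pretests; 72 starters; posttests 31 and 35 (all from Participants). The pretest split by arm is not given. Equal arms within cohorts of 22, 22 and 28 give 11 + 11 + 14 = 36 starters per arm. Starters had completed the pretest, so treatment pretests number 36 to 38 and control pretests 40 to 38. Assumed, because the documents are silent: pretest SD 1, posttest SD k, and r from 0.3 to 0.9.

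**The plan's own figure.** The only related figure is the 56 people for 80% power. It cannot be reproduced uniquely, because the effect-size metric, the test and r are not stated. A 2 by 2 within-between interaction with f = 0.25 needs 46 at r = 0.3, 34 at r = 0.5, and 56 only at r of about 0.15. Regression with f² = 0.15 and one tested predictor needs 55. Nothing below depends on the 56.

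**Step 1: variances.** With an unstructured covariance:
- Constrained model: k²(1 − r²)(1/31 + 1/35), where 1/31 + 1/35 = 0.06083.
- Interaction: the same quantity plus (1 − rk)²(1/36 + 1/40), where 1/36 + 1/40 = 0.05278. A 38/38 split gives 0.05263, which makes no material difference.

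The extra term is the price of the free pretest means. Example, r = 0.5 and k = 1: constrained 0.75 × 0.06083 = 0.0456; interaction 0.0456 + 0.25 × 0.05278 = 0.0588; ratio 0.78.

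**Step 2: results.** Power is for an assumed 0.5 SD difference (noncentral t, 64 df, two-sided 0.05). Equivalent completers are 66 divided by the variance ratio.

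| r | Interaction variance, k = 1 | Constrained variance, k = 1 | Saving, k = 1 | Equivalent completers | Power, k = 1 | Saving, k = 1.2 | Saving, k = 0.8 |
|---|---|---|---|---|---|---|---|
| 0.3 | 0.0812 | 0.0554 | 32% | 97 | 0.41 to 0.55 | 21% | 46% |
| 0.5 | 0.0588 | 0.0456 | 22% | 85 | 0.53 to 0.64 | 11% | 39% |
| 0.7 | 0.0358 | 0.0310 | 13% | 76 | 0.74 to 0.80 | 3% | 34% |
| 0.8 | 0.0240 | 0.0219 | 9% | 72 | 0.89 to 0.91 | 0% | 33% |
| 0.9 | 0.0121 | 0.0116 | 4% | 69 | 0.994 to 0.996 | 2% | 36% |

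The saving vanishes where rk = 1, which is r = 0.83 at k = 1.2. Simulation with the covariance estimated and equal SDs (3,000 trials each, r = 0.3, 0.5, 0.7) gave type I error 0.056, 0.052, 0.060 for the constrained model and 0.055, 0.048, 0.056 for the interaction.

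**Step 3: why not a random intercept.** That model forces one variance on both times. With complete pairs and k = 1.2 it fits (1 + 1.44)/2 = 1.22, against a true posttest variance of 1.44. At r = 0.8 its slope is 0.96/1.22 = 0.787. Its model-based variance is 1.22 × (1 − 0.787²) = 0.465, but the true variance is 1.44 − 2 × 0.787 × 0.96 + 0.787² = 0.548 (each times the same sample-size factor). The interaction's variance is 2.44 − 1.92 = 0.52, so the random-intercept version is about 5% worse. Its test is too liberal: 1.96 × √(0.465/0.548) = 1.80, a two-sided error of about 0.07. With the actual 76 and 66, its variance relative to the interaction is 0.79, 0.90, 1.00, 1.05 and 1.10 across the five values of r. Its type I error is about 0.07, against 0.05 for the interaction.

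**Step 4: the four people without a pretest.** With 36 treatment starters, at most two of the four can be treatment losses. The extreme is all four from control. If they differ from the rest of that arm by 1 SD at both times, the retained control mean shifts by 4/42 = 0.095 SD. The constrained model (k = 1) then has bias (1 − r) × 0.095: 0.067, 0.048 and 0.029 SD at r = 0.3, 0.5 and 0.7. Mean squared error is still lower than the interaction's: at r = 0.3, (0.0554 + 0.067²)/0.0812 = 0.74. If the four differed by 1 SD at pretest and only r SD at posttest, the constrained model is unbiased and the interaction carries a bias of that size.

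**Step 5: covariates.** A covariate fixed over time and entered as a main effect cancels from within-person change. In 400 simulated mixed-model trials (r = 0.5, equal SDs), adding one left the interaction's SD at 0.250. Dropping the condition main effect instead cut it to 0.218.

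**The case against.** The interaction is valid, answers the question asked about change, and is nearly immune to unequal SDs. The gain depends on an r that the documents do not give, and data collection is complete. All of that stands. It makes this a question of efficiency, and it is why the interaction should remain on show.

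The unnamed covariates also leave some doubt. Procedure places them in the demographic survey, apart from the pretest, so a pretest covariate looks unlikely but cannot be excluded.

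Four stronger readings are tempting and are not supported:
- That the plan ignores the pretest or gives a biased arm effect. It does neither; the pretest is the reference for change.
- That deleting one term from the lme4 random-intercept model is a free improvement. Step 3 shows that it can lose both precision and error control.
- That all four losses before the pretest could be from treatment. This conflicts with 36 treatment starters out of 38 randomised. The same counts do imply unequal losses before the start of the intervention (42 − 36 = 6 control, 38 − 36 = 2 treatment), so the assumption about losses should be stated openly.
- That the step outcome adds weight. A "percent change in the number of steps from baseline to the intervention" already contains the time contrast. How it was modelled is a separate clarification and is no part of this point.

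**Conclusion.** The point holds as one of precision. For outcomes measured at both times, the described interaction spends information on separate pretest means that randomisation makes unnecessary. At equal SDs the variance saving runs from 32% at r = 0.3 to 4% at r = 0.9, which is about 19 extra completers at r = 0.5 and 3 at r = 0.9. It is close to nil for r of 0.7 or more if the posttest SD is 1.2 times the pretest SD, and larger if the posttest SD is smaller.

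These figures rest on assumed correlations and SD ratios, on covariates that do not already include the pretest, and on losses before the pretest being unrelated to arm. Blinding and the week-3 start make that last assumption plausible, and the feasible extreme does limited harm. The change is worth making; it is not a correction of an invalid analysis.

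**What to change.** For each outcome measured at both times, fit one model to all 76 people with fixed effects for time, treatment at posttest (1 only for treatment-arm posttests) and the covariates, and no condition main effect. Use an unstructured 2 x 2 covariance from the outset, so that no choice is made after seeing the SDs. A GLS or repeated-measures mixed-model routine will fit it. An ordinary lme4 random-effects term will not: with two observations per person, a 2 x 2 random-effects covariance plus a residual variance is four parameters for three moments. A posttest-only ANCOVA has nearly the same precision but leaves out the 76 − 66 = 10 people without a posttest.

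Name the covariates and say how they enter. Report the number of pretests and the pretest means by arm, the SDs at both times and r.

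The cost is a change of fitting routine and no new data. The downsides should be stated: the model must be labelled as specified after data collection (completed March 2022), with the interaction shown alongside; the gain is small if r is high or the posttest SD is larger; and the assumption about the four losses must be made explicit.
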